Prior to initiation of the main study, a dose escalation study will be conducted. A cohort consisting of one healthy volunteer and one participant with POTS will be administered a dose of 50mg carbidopa every 6 hours for a total of five doses. If this dosage is well-tolerated (see next paragraph), a second cohort will be given five doses of carbidopa 100mg with 6 hours between doses. If this dosage is well-tolerated, a final cohort will take the proposed dose of 200mg carbidopa every 6 hours for five doses. All participants in the dose escalation study will also take placebo every 6 hours for five doses, according to a crossover design, and will undergo the same measurements and procedures as described below for the main study. However, additional blood draws and monitoring will be included.

Specific aims of Dose Escalation Study.

1. To assess tolerability of increasing doses (50mg, 100mg, 200mg) of carbidopa, as assessed by ECG, complete blood count (CBC), chemistry panel, liver function biomarkers, and a Psychiatric Symptom Questionnaire.
2. To assess plasma carbidopa levels after different doses of carbidopa.
3. To obtain preliminary data on the changes in plasma and urinary levels of catecholamines and urinary sodium excretion following oral administration of different doses of carbidopa.
4. To obtain preliminary data on the effect of oral administration of different doses of carbidopa on orthostatic changes in heart rate and blood pressure, as well as symptoms.
5. To compare the tolerability, as well as catecholamine, diuretic, and cardiovascular responses following orally administered carbidopa in participants with POTS with those of healthy volunteers.

To accomplish these aims:

- Pre-study assessments consist of 1) 12-lead ECG; 2) complete blood count (CBC) with platelets; 3) chemistry panel including albumin, total bilirubin, alkaline phosphatase, serum glutamic oxaloacetic transaminase (SGOT), and serum glutamic pyruvic transaminase (SGPT) to evaluate liver function; and 4) plasma carbidopa.
- Participants will be provided a 200 mEq/day sodium diet, free of methylxanthines and low in monoamines, by the kitchen of the Clinical Research Center (CRC).
- After achieving sodium balance on the study diet over 2-3 days, participants will collect urine over 24hr for baseline assessment of sodium and catecholamines and to confirm adherence to the study diet.
- On this day, the participants will be admitted to the CRC.

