- After at least a 1 day washout period, the study will be repeated with Treatment B. Treatment B consists of exactly the same regimen as Treatment A. The participant will be randomized to receive placebo or carbidopa (whichever was not given during Treatment A).

Throughout the dosing period, participants will be monitored (HR and BP measurement, Psychiatric Symptom Questionnaire, and questioning by study personnel 2hr after each dose) for adverse events, including allergic reaction, nausea, worsening hypotension or tachycardia, arrhythmia, neuroleptic malignant syndrome, hallucinations or other psychiatric symptoms. No more doses will be given to a participant who experiences an allergic reaction, arrhythmia, increased body temperature $>100.4^{\circ}\text{F}$, or $>38^{\circ}\text{C}$, changes in supine BP $>20\text{mmHg}$ or changes in supine HR $>30\text{bpm}$, hallucinations or psychiatric symptoms (as determined by our Psychiatric Symptom Questionnaire). Adverse events and post-study changes in ECG or laboratory values (in relation to pre-study assessments) following carbidopa and placebo will be summarized for each cohort. Adverse events will be defined according to the Common Terminology Criteria for Adverse Events, version 4.0 (CTCAE). [REDACTED]

[REDACTED], the Independent Medical Monitor (IMM) for this study, will review the data and use clinical judgment to decide whether to proceed to the next higher dosage of the dose escalation study. In general, a grade 2 event in more than one participant or a grade 3 event judged to be drug-related in any one participant will lead to study termination. Post-dose laboratory assessments may be repeated to confirm abnormalities.

Participants in the dose escalation study will not be allowed to also participate in the main study.

1.C. Detailed Description of Main Study:

This study will only be conducted if the results of the dose escalation study indicate that the 200mg dosage of carbidopa is well tolerated when given every 6hr for 5 doses. We will determine whether inhibition of renal

dopamine formation by carbidopa administration leads to a decrease in urinary excretion of dopamine and sodium and whether the response differs in POTS and control populations. Carbidopa effects will be compared to those of a matching placebo, and the sequence of treatments (carbidopa before placebo or placebo before carbidopa) will be randomized.

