paradoxically low in POTS in view of the reduced plasma volume. This indicates that sodium handling is perturbed in POTS. Several investigators have implicated dopamine in the control of natriuresis in other disorders. Approximately 50% of sodium excretion appears to be under dopaminergic regulation.

Uptake of dopa into the proximal tubule cells and its subsequent decarboxylation to DA are stimulated by a high salt diet. Carbidopa inhibits the activity of AADC in the periphery. By blocking the conversion of dopa to DA, it has the potential to attenuate the effects of the sodium load on renal DA production and urinary sodium excretion. However, since carbidopa also inhibits dopa decarboxylation in peripheral neurons, it can increase plasma dopa levels and the filtered load of dopa in the kidney. The final effect of carbidopa on renal DA production is therefore the result of increased substrate and decreased decarboxylation[12].

Recommended dosages of carbidopa for the treatment of Parkinson's disease, as Sinemet®, are at least 70-100 mg, up to 200 mg daily (AHFS Drug Information 2007). Yet, Durso et al.[6] speculated that "doses used in current practice" are not saturating for the decarboxylase enzyme. Kaufmann et al.[22] and Hershey et al.[15] administered one dose of 200 mg carbidopa to ensure that the decarboxylase was completely inhibited. Stokes et al.[30] proposed that more than one dose of carbidopa must be given to see an effect on renal salt handling. Based on this information and a carbidopa half-life of about 2 hours, we have chosen to administer 200 mg of carbidopa every 6hr. We believe that with repeated dosing of 200 mg, we will be able to assess the influence of decarboxylase inhibition on urinary sodium excretion. Nevertheless, since this dosage is higher than that which is FDA approved, we will first conduct a dose escalation study with 50mg, 100mg and 200mg of carbidopa to confirm that these dosages are well tolerate

[figure not shown]
[figure not shown]

Figure 3

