The following studies are designed to compare the influence of plasma dopa levels on plasma and urinary catecholamines in participants with POTS and healthy volunteers and to assess subsequent effects on sodium excretion. We will evaluate the roles of peripheral dopa and DA in POTS by comparing the effects of placebo and carbidopa on urinary DA and sodium excretion in patients and controls. Study participants will consume a relatively high-salt diet to "turn on" the dopaminergic regulation of sodium excretion. The dosage of carbidopa may be modified to attenuate or intensify the responses, not to exceed 1000mg in a 24hr period.

4. Study Design and Methods

We will determine whether inhibition of renal DA formation by carbidopa administration leads to a decrease in urinary excretion of DA and sodium and whether the response differs in POTS and control populations. Carbidopa effects will be compared to those of a matching placebo, and the sequence of treatments (carbidopa before placebo or placebo before carbidopa) will be randomized. The study is double-blinded. The investigational pharmacy at Vanderbilt Medical Center determines the randomization and the treatment order. The same crossover design is used for both the dose escalation and main studies.

Recruitment. The participants with POTS will be recruited for both dose escalation and main studies from patients referred to the Vanderbilt University Autonomic Dysfunction Center. Control participants will be recruited from healthy volunteers known to the Autonomic Dysfunction Center, through the ResearchMatch.org database, and through emails to the Vanderbilt community.

4.A Inclusion criteria

Healthy Volunteers

- Free of orthostatic symptoms
- No chronic medical conditions
- Free of medications with the potential to influence BP
- Non-smoking
- Ages between 18-60
- Males and females
- Able and willing to provide consent

POTS Participants

- Patients diagnosed with POTS by the Vanderbilt Autonomic Dysfunction Center based on the following stringent criteria: 1) history of daily orthostatic symptoms for at least 6 months; 2) increase in heart rate (HR) of at least 30 bpm with standing or a standing $HR \geq 120$ bpm; 3) absence of orthostatic hypotension (defined as a fall in blood pressure (BP) $>20/10$ mm Hg); and 4) absence of conditions, such as dehydration, substantial weight loss, or systemic illnesses, that could provoke orthostatic intolerance
- Non-smoking

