- In the morning, while still supine and NPO after the overnight sleep, HR and BP will be recorded with a Dinamap electrocardiographic and blood pressure (brachial cuff) recorder, and blood will be drawn for a basic metabolic panel, fractionated catecholamines, aldosterone and plasma renin activity. The participants will then stand for 10 minutes or for as long as they are able to tolerate. They may sit for short intervals if necessary. HR and BP will be measured at 1, 3, 5, and 10 minutes of standing, and an upright blood sample will be collected at 10 minutes for catecholamines, plasma renin activity, and aldosterone.
- The participants will be asked to void while recumbent, if able, or after the upright measurements, to end the first 24hr urine collection. Another 24hr urine collection will then be started for analysis of sodium, potassium and creatinine. This may take the form of one 24 hr sample or two 4 hr collection samples followed by a 16 hr sample collected from approximately 3 pm to 7am the following morning. The second schedule will facilitate comparison to urinary excretion after the final dose.
- Treatment A (Carbidopa 200mg or placebo) will be given orally following the void, at approximately 0700hr. Additional doses will be taken every 6 hours with the last dose at 0700hr the following morning. BP and HR will be measured 2 hours after each dose. Participants will remain on the CRC for monitoring.
- In the next morning, supine and standing HR and BP will be recorded with a Dinamap recorder, and the participants will be asked to void and collect the urine to end the 2nd 24hr urine collection.
- The final dose of study medication (Carbidopa 200mg or placebo) will be given orally following the void, at approximately 0700hr.
- Supine HR and BP will be measured by Dinamap and supine blood samples will be collected hourly for 4 hours after the 5th dose and at 8 hours after the treatment. Participants must rest supine for at least 30 minutes before each blood draw. These samples will be analyzed for catecholamines (all samples), carbidopa (at 2, 4 and 8hr) and plasma renin activity and aldosterone (only at 2 hr after treatment). In addition, a basic metabolic panel will be run for the 4-hour and 8-hr samples.

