Written informed consent will be obtained from each participant before any study-specific procedures or assessments are done and after the aims, methods, anticipated benefits, and potential hazards are explained. The participant's willingness to participate in the study will be documented in writing in a consent form, which will be signed by the participant with the date of that signature indicated. The investigator will keep the original consent forms and signed copies will be given to the participants. It will also be explained to the participants that they are free to refuse entry into the study and free to withdraw from the study at any time without prejudice to future treatment. Written and/or oral information about the study in a language understandable by the participant will be given to all participants.

See appendix 1a &1b

8.C Potential risks

1. There is the inconvenience of having to sleep on the CRC for several nights.
2. Intravenous catheter placement and blood sampling can cause bruising, pain and infection.
3. Collecting urine can be inconvenient and embarrassing.
4. Blood pressure measurements with a cuff on the arm can be uncomfortable.
5. Drawing blood for analysis can cause discomfort or bruising.
6. Standing upright may cause lightheadedness, blurred vision, rapid heartbeat, headache and nausea.
7. Carbidopa – only reported to have adverse effects when it is given with the drug levodopa for Parkinson's disease. Less common adverse effects are allergies, psychotic episodes, depression and dementia. However, the dosage used in this study is higher than typically administered. We will therefore do a dose escalation study to assess the tolerability of the 200mg carbidopa dose that we propose to use in the main study.
8. Consuming a sodium- and caffeine-controlled diet that needs to be picked up at the CRC might be inconvenient. If caffeine intake is stopped suddenly, participants might have headaches and fatigue for a few days.

8.D Protection against risk

Due to the dosage of carbidopa proposed for the main study, an IND (#108723) has been obtained by [name]. All procedures have been used previously by the staff of the CRC or ADC, and risks will be minimized by using trained, well-qualified personnel.

8.E Potential benefits of the proposed research to the participants and others

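### A sentence in Background lets the carbidopa dose be changed under a 24-hour cap alone, although the main study is cleared and written for 200 mg every 6 hours only

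*Combined protocol and SAP*

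**What the plan says.** **The gate.** Section 1.C makes the main study conditional on the escalation showing that "the 200mg dosage of carbidopa is well tolerated when given every 6hr for 5 doses". Section 3 gives the reason for that step: "since this dosage is higher than that which is FDA approved, we will first conduct a dose escalation study". Section 5.C adds that carbidopa has not previously been given at this dose or this often.

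**The main-study dose.** Sections 1.C, 2 (first aim) and 4.G all give 200 mg every 6 hours for five doses. In 4.G: "Treatment A (Carbidopa 200mg or placebo) will be given orally following the void, at approximately 0700hr". Section 8.C says that the escalation is done "to assess the tolerability of the 200mg carbidopa dose that we propose to use in the main study".

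**The conflicting sentence.** The last paragraph of section 3, which introduces the comparison of placebo and carbidopa in patients and controls, ends: "The dosage of carbidopa may be modified to attenuate or intensify the responses, not to exceed 1000mg in a 24hr period". It is not confined to the escalation.

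**Who decides on dose.** In 1.B the IMM uses clinical judgment "to decide whether to proceed to the next higher dosage of the dose escalation study". No other section assigns a decision about dose.

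**The concern.** The escalation exists because 200 mg every 6 hours lies outside approved use and prior experience. That reasoning applies at least as strongly to a larger single dose. Yet the section 3 sentence allows responses to be intensified, sets no limit per dose, and does not say who decides, on which response, when, or after whose review.

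Two things are at stake. The first is safety: a main-study participant could receive a single dose that no escalation participant received, with fewer checks than the 50 mg cohort had. The second is interpretation: a change in either direction during the main study would leave more than one carbidopa dose in a comparison planned as if there were one. It is also unclear how responses to carbidopa would be judged in time, since section 6 breaks the blind only at the end of the study.

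**Working it through.** **Inputs**
- Cap: 1000 mg in 24 hours (section 3, last paragraph).
- Dose times: 0700, 1300, 1900, 0100 and 0700 (Tables 1 and 3). The fifth dose falls exactly 24 hours after the first.
- Escalation doses: 50, 100 and 200 mg (1.B). Each level has one cohort: "A cohort consisting of one healthy volunteer and one participant with POTS".

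**Step 1: where the cap sits against the tested regimen.** Total = dose x number of doses counted. Largest dose allowed = 1000 / number of doses counted.

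| Counting rule | Doses counted | Total at 200 mg | Largest dose under the cap | Relative to 200 mg |
|---|---|---|---|---|
| Hour-24 dose counted | 5 | 5 x 200 = 1000 mg | 1000/5 = 200 mg | 1.00 |
| Hour-24 dose not counted | 4 | 4 x 200 = 800 mg | 1000/4 = 250 mg | 1.25 |

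Under the first rule the cap equals the top escalation regimen and leaves no room above it. Under the second it allows 250 mg per dose, and the five-dose course would total 5 x 250 = 1250 mg instead of 1000 mg. The protocol does not say which rule applies. No escalation participant receives more than 200 mg per dose.

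**Step 2: monitoring in the two parts.**

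| Check | Escalation (1.B, Table 1) | Main study (4.G, Table 3) |
|---|---|---|
| BP and HR 2 h after each dose | Yes | Yes |
| Psychiatric Symptom Questionnaire 2 h after each dose | Yes | Not listed |
| ECG, CBC and liver enzymes 2 h after dose 5 | Yes | Not listed |
| Metabolic panel 4 h and 8 h after dose 5 | Yes | Yes |
| Written criteria for stopping a participant's doses | Yes | Not listed |

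The stopping criteria in the last row begin "No more doses will be given to a participant who experiences an allergic reaction, arrhythmia" and appear only in 1.B. In the main study, 5.G provides for discontinuation after an unexpected reaction to treatment, without thresholds.

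**Step 3: the analysis.** Section 6 plans paired tests of placebo against carbidopa, two-sample tests of POTS against controls, and a mixed model with terms for time, treatment and group. None carries dose. Participants on a modified dose would be pooled with those on 200 mg, and if the doses differed between the groups, part of any difference in response could be due to dose. The documents give no dose-response information from which to size this, so no figure is attached.

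**The case against.** The strongest reply is that this is one loose line in Background. Every operative section gives 200 mg, no table implements a change, and 5 x 200 = 1000 mg is a natural origin for the cap. On that reading the sentence permits nothing above the tested regimen. Keeping the blind to the end also makes it hard to adjust an individual's dose by response. Oversight exists as well: an IND obtained because of the proposed dosage (8.D), inpatient monitoring, IMM review of serious, unexpected and related events as they occur (section 5), and IRB approval for protocol changes (8.G).

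Much of this stands. The five-dose count is plausible, and nothing shows an intention to exceed 200 mg. But the sentence is current text, and it states a permission. If five doses are counted, there is nothing left to intensify from 200 mg at 6-hourly dosing, so that reading fits the wording only if the increase starts from a lower dose. The safeguards respond to events or to protocol changes. None plainly governs a modification that the protocol already allows.

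Three stronger readings are tempting and not supported:
- **That the protocol plainly permits an untested dose.** At 6-hourly dosing this depends on leaving out the hour-24 dose, which the text neither says nor excludes.
- **That fewer, larger doses at longer intervals are foreseen.** A cap on the daily total does not rule them out, but the sentence does not mention the interval. The procedures give 6 hours throughout, and section 3 bases the regimen partly on the half-life of about 2 hours.
- **That the main study could open without IMM involvement.** No sentence names who opens it, but section 6 sends each cohort's summary to the IMM, and the termination guide in 1.B covers the 200 mg cohort.

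**Conclusion.** The concern holds as an internal conflict with a safety consequence. The gate and the procedures cover one regimen, while section 3 allows the dose to move in either direction under a cap on the 24-hour total. The possible excess at 6-hourly dosing is nil if the hour-24 dose is counted and 50 mg per dose (25%) if it is not. In the second case the higher dose would come with no escalation cohort, stated criterion or IMM review, and with the lighter main-study monitoring.

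The analysis point does not depend on how 24 hours is counted. Any change during the main study, including a reduction, would mix doses without a term for dose. Its size cannot be given from the documents.

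The size given assumes that 6-hourly dosing is kept. Because the procedures consistently say 200 mg, use of the permission is a possibility, not an expectation. The change is worth making because it is cheap and removes an avoidable risk.

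**What to change.** Replace the last sentence of section 3 with:

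> The main-study dose is fixed at 200 mg every 6 h for five doses in both groups. No single dose may exceed 200 mg; a higher dose requires a further escalation cohort, IMM review and an IRB-approved amendment. Any lower dose is set after the escalation and before the first main-study participant is randomized, and applies to both groups.

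This settles the 24-hour count, keeps the main study within what the gate clears, and leaves one carbidopa dose in the comparison. It adds no participants or measurements to the planned trial.

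The cost is flexibility. If 200 mg lowered urinary dopamine too little, raising the dose would need an amendment and at least one more cohort of two, with a minimum of 9 days per participant on the schedule in 4.E.
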